# 3 Introduction

#### Overview

## The problem: I am feeling ill during the weekend, where should I go?

When confronted with an unexpected illness during the weekend, patients can go either to the emergency department (ED) of a hospital or to the general practitioner (GP) on call. In Flanders, the GPs often organise this on call service for a specified region in a central location called General Practice Cooperatives (GPC, "Wachtpost" in Dutch). Patients do not know the characteristics of these different out of hours (OOH) services and find it hard to estimate the urgency of their own complaints. Therefore, many patients with presentations suitable for primary care go directly to the ED. This leads to additional costs for both government and patient, long waiting times at the ED and a high workload for the emergency physicians in Flanders.

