# Hypotheses and Research questions

#### Medical aspect

Our primary hypothesis: the extended triage intervention will lead to a substantial increase in the proportion of patients seen by the GP.

Without the intervention, all study patients can be divided in three categories: seen by ED, seen by GPC and left without being seen (after the triage). By adding the compliance of the patient to the allocation advice we get the following table:

	Patient goes to GPC	Patient goes to ED	Left without being seen
Advice GPC	Compliant patient GPC	Non-compliant patient GPC	Left without being seen type 1
Advice ED	Non-compliant patient ED	Compliant patient ED	Left without being seen type 2

Table 1: patient categories

The proportion of study patients seen at the GPC is a combination of patients compliant to a GPC advice and patients not compliant to an ED advice. The latter category will probably be small.

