#### Design of the clinical trial

#### A controlled longitudinal prospective intervention trial

To answer the above-mentioned research questions we need a longitudinal prospective intervention trial.

To allow definitive conclusions for our questions we need a control group. Historical controls will have too much confounding (not all data is available, the ED was organised in a different way, the GPC was unknown for many patients). Individually randomised controls are impossible from a practical point of view and because of contamination (patients will talk to each other and will not understand why some get a GPC advice and others not). Finally, randomisation by shift is not possible because they overlap in time. Therefore, randomisation is only possible by weekend. We will roll out one control weekend out of every four intervention weekends.

During a control weekend, all data registration and collection will be the same as during intervention weekends but we will not inform patients about their allocation advice. The emergency physician will see all patients deciding to stay at the ED, without influence of the triage advice. As in standard clinical care, patients will have the right to change their mind and go spontaneously to the GPC. Another difference is the communication to the patient: during intervention weekends, we will inform them about the intervention using leaflets and broadcasting in the waiting room of the ED. During control weekends, we will only inform about MTS-triage in general but no about the GPC. We will always mention the iCAREdata opting-out procedure.

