# Methodology for the financial aspects

Resources are scarce and therefore it is essential to look at both outcome and resource use when introducing new treatments or treatment paths. This project incorporates both sides. We will use HIS expenditure data (including the share paid by the patient) to get a first insight in the changes in resource use due to the extended triage. Expenditures will be limited to the expenditures of the OOH consultation. In this way, we gain insight in the short-term impact of the new triage system on medical costs from the point of view of the patient and the HIS. For this aspect, we only focus on ambulatory patients (not admitted to the hospital). Although some inpatients can also present at the ED; admitted patients have far more complicated costs and they are not the focus of this project.

In our research we will make use of a cluster randomized trial to get an unbiased estimate of the difference in expenditures due to the extended triage. Randomization allows to measure the impact of the extended triage on average expenditures per patient (research question 9) or specific types of average expenditure per patient (research question 11) by comparing these average expenditures per patient between the intervention weekends and the control weekends. Information on the expenditures of consultations of the GPC are collected in the iCAREdata database. Expenditures generated by the ED are not yet routinely collected for research purposes, but billing data are available and these will be used. We will calculate the averages and use a t-test to test statistical significance. Medical bills also contain detailed information of the nomenclature codes (these are the codes used by the HIS, describing reimbursed care and reimbursement tariffs), performed during an ED visit. We will aggregate these interventions in similar groups such as consultation fees, medical imaging, clinical biology and so on. We will then compare these average expenditures per patient for the various aggregates between the intervention weekends and the control weekends (research question 10) and use a t-test for statistical significance.

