For research question 12 we will perform a multivariate regression analysis, explaining the expenditures (dependent variable) with three sets of explanatory variables: general background characteristics of the patient (age, sex, insurance status), diagnostic information (urgency code, chosen eMTS flowchart) and system characteristics (occupancy rate ED, time of the day, triage nurse, intervention or control weekend). The coefficient for the dummy variable indicating an intervention weekend then gives the impact of the extended triage. It should confirm the effect found in 8. The inclusion of control variables, when estimating the impact in our regression, however reduces residual standard deviation and thus improves the precision

of the estimate. The coefficients on the other variables give a further insight in the additional determinants of expenditures. The regression analyses will be performed on the computer of the data manager using STATA.

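### The regression for research question 12 adjusts for ED occupancy, which triage can change, yet reads the intervention coefficient as the impact of extended triage

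*Combined protocol and SAP*

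**What the plan says.** Under Methodology for the financial aspects, the regression for research question 12 has three sets of explanatory variables. The third is "system characteristics (occupancy rate ED, time of the day, triage nurse, intervention or control weekend". So ED occupancy enters beside the intervention indicator. The plan then says "The coefficient for the dummy variable indicating an intervention weekend then gives the impact of the extended triage", adds "It should confirm the effect found in 8", and credits the control variables only with improving precision. Of the rest of the model it says "The coefficients on the other variables give a further insight in the additional determinants of expenditures".

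The same section gives the unadjusted comparison the same target: "Randomization allows to measure the impact of the extended triage on average expenditures per patient (research question 9". Both analyses are therefore presented as estimates of one quantity.

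On design, the plan states "Therefore, randomisation is only possible by weekend". The primary hypothesis, under Medical aspect, is that "the extended triage intervention will lead to a substantial increase in the proportion of patients seen by the GP". The Introduction names, among the consequences of primary-care patients going to the ED, "long waiting times at the ED and a high workload for the emergency physicians in Flanders", and research question 6 studies the shift in workload. The plan does not define the occupancy rate, does not say when it is measured, and nowhere qualifies the coefficient as conditional.

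**The concern.** Adjusting for a covariate that the intervention cannot alter, such as age or sex, improves precision and leaves the target of a linear model unchanged. Occupancy is not of that kind. It arises inside a weekend that has already been allocated, and the intervention is meant to move patients out of the ED. Measuring it at each patient's arrival does not help, because earlier patients in the same weekend have already been exposed.

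If triage lowers occupancy and occupancy affects what is billed, holding occupancy fixed removes part of the effect from the coefficient. The adjusted figure could then understate or overstate the saving. Because the plan expects agreement with the unadjusted result, a gap could be taken as failed confirmation when it comes from the adjustment alone.

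**Working it through.** The plan gives no effect size, standard deviation or target figure for research question 12, so there is nothing of its own to reproduce. The check is a decomposition followed by an illustration.

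**Decomposition.** Let a be the change in occupancy caused by the intervention and b the cost slope on occupancy. In a linear model, total effect = effect at fixed occupancy + a × b. The gap between the two coefficients is a × b, and it is zero if a = 0 or b = 0.

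**Inputs from the documents**
- 8000 weekend presentations in 2016 (Recruitment strategy and expected dropout).
- 15 exclusions per weekend, and opening from Friday 7 pm to Monday 6 am, which is 5 + 24 + 24 + 6 = 59 h (Inclusion and Exclusion).
- One control weekend a month (Introduction, Aim of this project), taken as 12 control and 40 intervention weekends. The design section's ratio would give roughly 10 to 13 controls.

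Eligible patients per weekend: 8000/52 − 15 = 138.8, assuming that the 8000 includes those excluded. Rate: 138.8/59 = 2.353 per hour.

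**Assumed inputs:** share diverted, mean ED stay, and a cost slope of EUR 0.5 to 2 per patient present, of either sign.

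**Fall in occupancy and resulting gap.** The fall in mean occupancy follows from Little's law: rate × diverted share × stay. The fall met by arriving patients was simulated (3,000 weekends, time-varying arrivals, occupancy counted at each arrival). It is larger because more patients arrive at busy times.

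| Diverted, stay | Fall in mean occupancy | Fall at arrival | Gap at EUR 0.5 | Gap at EUR 2 |
|---|---|---|---|---|
| 5%, 2 h | 2.353 × 0.05 × 2 = 0.24 | 0.279 | 0.14 | 0.56 |
| 10%, 3 h | 2.353 × 0.10 × 3 = 0.71 | 0.838 | 0.42 | 1.68 |
| 20%, 4 h | 2.353 × 0.20 × 4 = 1.88 | 2.075 | 1.04 | 4.15 |

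**Middle case, with EUR 60 assumed saved per diverted patient.** Least-squares coefficients, adjusting for time of day, in EUR per patient:

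| Cost slope | Without occupancy (total) | With occupancy | With minus without |
|---|---|---|---|
| +2 | −7.66 | −5.98 | +1.68 |
| 0 | −5.98 | −5.98 | 0 |
| −2 | −4.31 | −5.98 | −1.67 |

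In every case the difference equalled minus (fitted slope × fitted occupancy difference), as the decomposition requires.

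**A shared weekend factor.** A separate simulation (52 weekends, 12 control, 139 patients each; all effects assumed) let an unmeasured weekend factor drive both occupancy and cost. With an effect at fixed occupancy of −10 and a total of −15, the model with occupancy gave −7.5, which is neither. The model without occupancy gave −14.8. So even the label of a direct effect would need further assumptions.

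**The case against.** The strongest reply is that the gap needs two links, and the documents establish neither. Occupancy is undefined, and a count of registrations would not fall, since every included patient registers at the ED before triage. No passage says that occupancy changes the bill. The unadjusted contrast for research question 9 already carries the randomised estimate, and research question 12 asks about determinants, where occupancy belongs. The plan attaches no test or decision to the expected confirmation, and the analysis is run only if the reconstructed bills prove valid. All of this stands, and it confines the point to how one coefficient is read.

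The gap is also modest against sampling error. With the assumed residual SD of EUR 100, the simple standard error is 100 × √(1/5552 + 1/1666) = EUR 2.8, a 95% half-width of about EUR 5.5 before clustering. Every illustrated gap lies inside that. The simulation also applies the cost slope to patients treated at the GPC, which probably overstates the gap a little, and it uses all eligible patients although the financial analysis covers ambulatory patients only. These points limit the size. But both coefficients come from the same patients, so a systematic gap between them can show even when each interval is wide.

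It can further be said that urgency code, flowchart and triage nurse are recorded after allocation too, by unblinded staff. They differ in kind: they are settled at triage before any advice takes effect, registration is the same in both arms, and late notice to staff guards against shift switching. Diversion itself moves occupancy.

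Finally, one could simply label the coefficient as conditional. That would correct the reading but leave no covariate-adjusted estimate of the total effect, which is what the plan says it wants.

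**Conclusion.** The concern holds. As specified, the intervention coefficient for research question 12 is an effect conditional on ED occupancy, and the plan reads it as the total impact. The two coincide only if triage leaves the occupancy measure unchanged or occupancy does not affect expenditure. The plan's own primary hypothesis makes the first unlikely for a measure of patients present; the second is left open.

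Size and sign cannot be derived from the documents. The range of EUR 0.14 to 4.15 per patient rests on the assumed diversion, stay and cost slopes. The harm is limited to interpreting research question 12 and its comparison with research question 9; the unadjusted contrasts for research questions 9 and 11 are untouched. It should be corrected, but it does not threaten the trial's main results.

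Separately, the reference to the effect found in 8 is an editorial slip: research question 8 concerns return visits, and the expenditure contrast is research question 9.

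**What to change.** Replace the sentence that equates the coefficient with the impact by:

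> The adjusted impact of extended triage is the intervention-weekend coefficient from this regression without ED occupancy, with all other listed covariates kept as pre-specified. The full model, including ED occupancy, is reported separately as the determinants analysis; its intervention coefficient is conditional on occupancy and is not read as the impact.

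State how and when occupancy is measured, and change the reference from 8 to research question 9.

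The cost is one extra model on data already planned, and possibly some precision, because occupancy also absorbs chance differences in demand between few control weekends. This was simulated with 400 replicates of 40 intervention and 12 control weekends, 10% diverted, a 3 h stay, residual SD EUR 100 and weekend demand CV of 0 to 20%, all assumed except the weekend counts. Leaving occupancy out changed the SD of the coefficient as follows:

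| Cost slope (EUR) | Change in SD |
|---|---|
| 0 | −0.7% to 0% |
| 1 | −0.3% to +5.9% |
| 2 | +3.4% to +12.8% |

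The worst case is not trivial: 1.128² = 1.27, equivalent to needing about 27% more data.

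If adjustment for demand is wanted in the impact model, an option is to pre-specify the number of ED registrations in a fixed window before arrival, which diversion after registration does not change. In the simulation this kept the SD within about 1% of the occupancy-adjusted model without moving the estimate. At slope 2 and CV 20% it gave −7.66, against −7.62 with neither covariate and −6.01 with occupancy.
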